8.4. Data Monitoring Committee

An external, independent Data Monitoring Committee (DMC) comprising physicians, scientists and a biostatistician will review the study data at a meeting after all subjects in the first cohort have been enrolled and reached Visit 4 (Day 14 ± 3 days), and after completion of the second cohort. Additionally, ad hoc meetings to assess individual exacerbations of CD or UC meeting Common Terminology Criteria for Adverse Events (CTCAE) Grade 3 or greater as defined in [Section 8.5](#) may be held. The DMC's role is to protect the interests of the subjects in the study and those still to be entered in the study by reviewing information such as safety, tolerability, pharmacokinetic and efficacy data. The DMC's meeting schedule may be adjusted based on recommendations made by the DMC, the amount of incremental safety data, and other practical considerations. The data provided to the DMC may not be monitored and will not be considered "clean" until the database is locked at the completion of the study.

Possible outcomes of the DMC review can include one of the following recommendations:

- Study can continue
- Study can continue with modifications
- Study is to be terminated

Data Monitoring Committee recommendation will be documented in meeting minutes which will include, at a minimum:

- List of meeting participants
- Summary of data considered during the meeting
- Summary of the DMC recommendation regarding further dose cohorts, including any concerns raised

The sponsor is responsible for the decision to continue, modify or terminate the study. A copy of the DMC meeting recommendation and sponsor decision will be sent to the study sites upon completion and prior to administration of the next subject dose in the second cohort.

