The total duration of participation is approximately 26 weeks. Subjects will be required to visit the study center up to 12 times inclusive of 1 additional follow-up safety visit. During the study, subjects will participate in safety and efficacy assessments as well as pharmacokinetic blood sampling; DcR3 genotyping (CD only); measurement of LIGHT (Lymphotoxin-like, exhibits Inducible expression, and competes with Herpes Virus Glycoprotein D for Herpesvirus Entry Mediator, a receptor expressed by T lymphocytes), selected cytokines; ribonucleic acid (RNA) sequencing; flow cytometry of peripheral blood leukocytes; and quality of life assessment. Subjects currently receiving treatment with biologic therapies will be required to participate in a wash-out period, during which biologic treatment will be discontinued.

Number of patients (planned):

Approximately 14 total subjects will be enrolled as follows:

- 4 subjects with CD in the 1 mg/kg cohort
- 4 subjects with CD in the 3 mg/kg cohort
- 6 subjects with UC in the 3 mg/kg cohort

Diagnosis and main criteria for inclusion:

Inclusion criteria - Crohn's Disease:

1. Subject is able to speak English fluently and has provided written informed consent for this study.
2. Subject is male or female, ≥ 18 to ≤ 75 years of age.
3. Subject has a documented diagnosis of CD via endoscopy/colonoscopy and histological confirmation. Prior documentation of histological confirmation is acceptable.
4. Subject has moderate to severe, active CD as evidenced by Simple Endoscopy Score for Crohn's Disease (SES-CD) score of ≥ 7 .
5. Subject has failed treatment with an approved therapeutic dose of an anti-TNF α monoclonal antibody treatment with either no initial response (primary non-responder) or an initial response to induction with subsequent lost response (secondary non-responder) as defined in the protocol.
6. Subject can be receiving concurrent treatment with an oral corticosteroid, and/or azathioprine or 6-mercaptopurine (6-MP) or methotrexate (MTX) as defined in the protocol.
- 7.
8. Subject agrees to be genotyped at the DcR3 locus.

Exclusion criteria - Crohn's Disease:

1. Subject has a diagnosis of ulcerative colitis (UC) or indeterminate colitis.
2. Subject is unable to tolerate or unwilling to undergo study procedures including endoscopy and biopsy during the study.
3. Subject with signs or symptoms of bowel obstruction with small bowel imaging supporting obstruction.

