8. INVESTIGATIONAL PLAN

8.1. Overall Study Design

This is a Phase 1b, multi-center, open-label, dose-escalation, signal-finding study to evaluate the safety, tolerability, PK and short-term efficacy of MDGN-002 in adults with moderate to severe, active CD or UC who have previously failed anti-TNF α treatment.

Four subjects with Crohn's disease who satisfy all eligibility criteria will be enrolled in each of 2 dose cohorts. The first cohort will receive MDGN-002 1.0 mg/kg SQ every 14 (q14) days. Dose escalation will proceed after all subjects in the first cohort have been enrolled and reached Visit 4 (Day 14 \pm 3 days), the safety data from those subjects has been reviewed by the Data Monitoring Committee, and a decision has been made to progress to the second cohort (see [Section 8.4](#)). The estimated dose escalation for the second cohort is 3.0 mg/kg SQ q14 days, if permitted by safety data review. After dose escalation has taken place 6 additional patients with UC will also be enrolled in the 3 mg/kg cohort.

Each subject's participation will include a screening period, which if required includes a wash-out period for subjects who have received biologic treatment within 12 weeks of the Screening Visit. With the exception of subjects requiring wash-out of the biologic certolizumab pegol (Cimzia), only those subjects without detectable biologic levels after 8 weeks of wash-out will be allowed to enter the study after confirmation of undetectable levels; all other subjects (including those receiving certolizumab pegol [Cimzia]) will be required to complete a full 12-week wash-out period. The wash-out period includes the time period from the last dose received prior to the Screening Visit. Subjects not requiring a biologic wash-out period will be allowed to enter the study after review and confirmation of eligibility at screening. Screening is followed by an 8-week, open-label treatment period, and a safety follow-up visit approximately 4 weeks after the last dose. The maximum study duration is 26 weeks.

Study visits will occur at screening and on Days 0, 7, 14, 21, 28, 35, 42, 49 and 56. The safety follow-up visit will occur on Day 84. The Schedule of Assessments is shown in [Table 1](#).

Table 1 Schedule of Assessments

Assessment or Procedure	Screening Period				Open-Label Treatment Period										Safety Follow-up	

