8.7. Number of Subjects

Four subjects with CD will be enrolled in each of the 2 planned dose cohorts for a maximum of 8 study subjects with CD. Additionally, 6 subjects with UC will be enrolled in the 2nd dose cohort. Subjects who withdraw from the study prematurely prior to a third dose may be replaced.

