10. TREATMENT OF SUBJECTS

10.1. Description of Investigational Product

A description of the investigational product is provided in [Section 11.1](#)

Subjects in each dose cohort will receive the investigational product as a single SQ injection in the abdomen in a zone of 4 to 10 cm from the umbilicus with the injection site rotated with each subsequent dose. The dose of MDGN-002 will be administered on Days 0, 14, 28, and 42. After Day 0, injections must occur within \pm 3 days of the scheduled 14-day intervals.

Subjects in the first dose cohort will receive MDGN-002 1.0 mg/kg for the entire 8-week, open-label treatment period. Data from this cohort will be reviewed by the Data Monitoring Committee as described in [Section 8.4](#) before subjects in the second dose cohort can be treated.

Eligible subjects in the second dose cohort will receive MDGN-002 3.0 mg/kg for the entire 8-week, open-label treatment period. Data from the second cohort will be reviewed, as described in [Section 8.4](#), after all subjects have completed the treatment period and its associated assessments.

Any quality issue noticed with the receipt or use of an investigational product provided by the sponsor (deficiency in condition, packaging, appearance, pertaining documentation, labeling, expiration date, etc.) should be promptly communicated to the sponsor, who will investigate.

A potential defect in the quality of investigational product provided by the sponsor may be subject to initiation of a recall procedure by the sponsor. In this case, the investigator will be responsible for promptly addressing any request made by the sponsor, in order to recall the investigational product and eliminate potential hazards.

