13. DATA MONITORING COMMITTEE

An external, independent Data Monitoring Committee (DMC) comprising physicians, scientists and a biostatistician will review the study data at separate meetings after enrollment in the first and second cohorts, respectively.

The DMC's role is to protect the interests of the subjects in the study and those still to be entered in the study by reviewing information such as safety, tolerability, pharmacokinetic and efficacy data.

Additional details will be outlined in the DMC charter.

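### The second scheduled DMC review comes after all ten 3 mg/kg subjects have finished treatment, so on the default schedule it cannot change anyone's dosing

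*Protocol*

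**What the plan says.** Protocol 8.4 sets two scheduled DMC reviews: "after all subjects in the first cohort have been enrolled and reached Visit 4 (Day 14 ± 3 days), and after completion of the second cohort". Protocol 10.1 says that second-cohort data are reviewed "after all subjects have completed the treatment period and its associated assessments".

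The UC subjects belong to that cohort. Protocol 8.7 states that "6 subjects with UC will be enrolled in the 2nd dose cohort", and Protocol 8.1 gives the condition for their entry: "After dose escalation has taken place 6 additional patients with UC will also be enrolled in the 3 mg/kg cohort". Escalation itself depends on the first review, which covers CD subjects at 1 mg/kg.

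SAP 13 describes the timing differently: the committee "will review the study data at separate meetings after enrollment in the first and second cohorts, respectively".

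Protocol 8.4 gives the DMC the task of protecting subjects in the study and those yet to enter. It lists three possible recommendations (continue, continue with changes, terminate) and requires the recommendation and the sponsor's decision to reach sites before the next dose is given in the second cohort.

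Other oversight during cohort 2:
- individual and study stopping criteria (8.5.1, 8.5.2);
- DMC review, at the first available date, of Grade 3 or worse exacerbations of Crohn's disease (8.5.2);
- weekly review by each investigator of their own site's data, with the medical monitor going to the DMC as needed (8.3);
- optional ad hoc DMC meetings on CD or UC exacerbations, and a meeting schedule that may be adjusted (8.4);
- continual monitoring of the open-label data (13.1.2).

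**The concern.** A scheduled review protects subjects only if its recommendation can still change something. The second review is placed where treatment at 3 mg/kg is over and no further cohort is planned, so none of its three possible recommendations has a dosing or enrolment decision left to act on. Only the first review can serve the purposes that 8.4 sets out, and it sees no 3 mg/kg data.

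Safety is the primary objective, and most subjects receive the higher dose. The UC subjects start at that dose with no lower-dose UC cohort before them and no scheduled look at how the CD subjects tolerated it. A pattern of events that stays below the automatic stopping thresholds would reach the DMC during dosing only if someone chose to raise it.

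**Working it through.** **Inputs.** CD: "Four subjects with CD will be enrolled in each of the 2 planned dose cohorts for a maximum of 8 study subjects with CD" (Protocol 8.7). UC: 6, all at 3 mg/kg. Doses: four per subject, on Days 0, 14, 28 and 42 (Protocol 10.1). Visit 4 is Day 14 ± 3.

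**Plan's own figure.** The synopsis says "Approximately 14 total subjects will be enrolled as follows". 4 + 4 + 6 = 14, which reproduces.

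**What the second review can affect as written.** Cohort 2 has 4 + 6 = 10 subjects and 10 × 4 = 40 planned doses, of which 6 × 4 = 24 are in UC subjects. The last dose is on Day 42 and the treatment period ends on Day 56. Once all ten have completed it, 0 doses remain. Subjects still to enrol: 14 − 4 − 10 = 0.

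**What the first review sees.** Four CD subjects at 1 mg/kg. The last to reach Visit 4 may have had only one dose. No subject has had 3 mg/kg.

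**The two timings side by side.**

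| Source | Second review | Could 3 mg/kg dosing still change? | Have all UC subjects already entered? |
|---|---|---|---|
| Protocol 8.4 and 10.1 | after the cohort completes | No | Yes |
| SAP 13 | after enrolment in the cohort | Possibly, for late enrollees | Yes |

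**What the cohort 1 trigger would give at 3 mg/kg.** Suppose the review is due when the first four subjects dosed at 3 mg/kg have all reached Visit 4, enrolment is not paused, and nobody withdraws.
- Most favourable case: all four start together, Visit 4 doses are not yet given, and nobody else has started. Doses given = 4 × 1 = 4, so 40 − 4 = 36 remain. If the Visit 4 doses have been given, 40 − 8 = 32 remain.
- Least favourable case: the first three have finished, and the fourth and the other six all started on the same day and have had two doses. Doses remaining = 7 × 2 = 14.
- Subjects not yet enrolled: 0 to 6.

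These counts apply on the trigger date. In the least favourable case a meeting two weeks later leaves 7 × 1 = 7 doses, and one four weeks later leaves none, so the meeting must be prompt.

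**Sensitivity of a look at four subjects.** The documents give no event rates; those below are assumed.

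| Assumed per-subject rate | P(at least 1 event in 4) = 1 − (1 − p)^4 | P(at least 1 event in 10) | P(at most 1 event in 4) |
|---|---|---|---|
| 10% | 0.34 | 0.65 | 0.95 |
| 20% | 0.59 | 0.89 | 0.82 |
| 30% | 0.76 | 0.97 | 0.65 |

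The last column is the chance that the rule of two subjects with the same listed Grade 3 event does not fire on those four alone. With no events in four, the one-sided 95% upper bound is 1 − 0.05^(1/4) = 0.53.

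**The case against.** The strongest reply is that cohort 2 is well supervised without a second timely meeting. Hard stopping rules run throughout, and one listed Grade 4 event stops the study. DMC review of severe Crohn's exacerbations is mandatory. Section 8.4 lets the committee move its meetings as safety data accumulate, so an earlier look needs no amendment. The DMC charter, to which SAP 13 defers, may already provide one, and it is not among the documents. All of this stands, and it rules out any reading that 3 mg/kg is given without oversight. But the adjustment and the ad hoc meetings are optional, weekly review is by site, and the mandatory trigger in 8.5.2 names only Crohn's disease although 8.4 speaks of CD or UC.

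Two stronger inferences are tempting and should not be drawn.
- A reader might say that the schedule contradicts the design rationale in 8.6. That section speaks of evaluating small numbers before moving to the next dose level. Since 3 mg/kg is the last level, the review before escalation satisfies it.
- A reader might multiply an assumed event rate by the six later subjects: 6 × 0.20 = 1.2, or 6 × 0.30 = 1.8 unreviewed Grade 3 events. That ignores the stopping rule. Given at most one event in the first four, and with events seen one subject at a time, the expected number before the rule stops the study is about 0.91 or 1.10. The rule itself fires within those six with probability 0.54 or 0.77.

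It is also fair to say that without an enrolment pause an earlier review does not control UC entry: all six may already be enrolled when it meets.

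**Conclusion.** The point holds for scheduled DMC reviews under the protocol's wording. The second review can affect 0 of 10 subjects, and UC subjects enter with no scheduled DMC look at 3 mg/kg data under either document's timing. The zero is a property of the default schedule. It would not be strict under SAP 13, or if the DMC used its freedom to meet earlier.

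The mismatch is with the DMC's own stated role in 8.4. It does not show that subjects are unprotected or that any dose is unsafe. The redacted clinical background in 6.2.3 prevents any judgement of earlier human exposure relative to 3 mg/kg.

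This is a change that should be made: the remedy is cheap and turns a review that cannot affect dosing into one that can. The size of the gain depends on enrolment pace, and the sensitivity figures rest on assumed event rates.

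**What to change.** - In Protocol 8.4 and 10.1, schedule the DMC review of 3 mg/kg data for when the first four subjects at that dose have reached Visit 4, the trigger already used for cohort 1. Enrolment need not pause. Hold the meeting promptly.
- Keep any end-of-cohort look as a final review. SAP 5.3 gives a half-life of 18 to 27 days against a 14-day dosing interval, so a Day 14 look may cover one dose per subject and will not see exposure after repeated dosing.
- Reconcile SAP 13 with Protocol 8.4 and 10.1, and carry the same timing into the DMC charter.
- Reconcile 8.4 with 8.5.2 on whether the event-triggered DMC review covers UC as well as Crohn's exacerbations.

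Cost: protocol, SAP and charter wording, and one short meeting moved or added, on data already collected. No extra subjects, procedures or visits are needed.

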8.5. Individual Subject and Study Stopping Criteria

8.5.1. Individual Subject Stopping Criteria

The following individual subject stopping criteria will be used during the study and will be assessed starting post-dose at Visit 2:

- A subject develops a CTCAE Grade 3 or higher of the following:
 - Injection site reactions
 - Opportunistic infections (i.e. tuberculosis)
 - Hypersensitivity reactions (e.g. allergic reactions, anaphylaxis or cytokine release syndrome)
 - Malignancy
 - Decreased white blood cell count
 - Decrease neutrophil count
 - Decreased platelets
 - Colonic or ileal hemorrhage
 - Colonic, ileal or small intestine obstruction
 - Colonic, ileal or small intestine perforation
 - Colonic, ileal or small intestine stenosis
- A subject will also be stopped if liver enzymes are:
 - ALT or AST >8x ULN
 - ALT or AST >5x ULN for more than 2 consecutive weeks or
 - A single subject ALT or AST >3x ULN with the appearance of fatigue, nausea, vomiting, right upper quadrant pain or tenderness, fever, rash and or eosinophilia (>5%).

Note: subjects who exhibit ALT or AST >3x ULN without appearance of any of the above symptoms must have repeat testing within 48-72 hours to confirm abnormality and determine direction (increase or decrease) from the original value.

- A subject will be stopped if Hy's Law is detected (i.e. ALT or AST >3x ULN and total bilirubin >2x ULN and no other reason can be found to explain the combination of increased AT and TBL, such as viral hepatitis A, B, or C; preexisting or acute liver disease; or another drug capable of causing the observed injury).

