8.3. Safety Data Review

Each investigator will review all available safety data collected at their site on a weekly basis, and communicate any safety concerns to the sponsor medical monitor. The sponsor medical monitor will review all relevant safety findings with the coordinating principal investigator and DMC as needed.

Special attention will be paid to adverse drug reactions observed in the MDGN-002 preclinical study as well as other common adverse reactions seen with other biologic treatments which include:

MDGN-002 preclinical observation:

- Injection site reactions

Adverse reactions observed with other biologic treatments:

- Potential for increased infection including opportunistic infections (such as tuberculosis)
- Hypersensitivity reactions (including anaphylaxis)
- Immunogenicity
- Malignancy
- Impaired immunization
- CD exacerbation

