8.5.2. Study Stopping Criteria

The following study stopping criteria will be used during the study:

- The study will be stopped if two or more subjects develop the same CTCAE Grade 3 or if one subject develops a CTCAE Grade 4 of the following:
 - Injection site reactions
 - Opportunistic infections (i.e. tuberculosis)
 - Hypersensitivity reactions (e.g. allergic reactions, anaphylaxis or cytokine release syndrome)
 - Malignancy

- Decreased white blood cell count
 - Decrease neutrophil count
 - Decreased platelets
- The study will be stopped if two individual subjects develop any of the following liver toxicities:
 - ALT or AST >8x ULN
 - ALT or AST >5x ULN for more than consecutive 2 weeks or
 - ALT or AST >3x ULN with the appearance of fatigue, nausea, vomiting, right upper quadrant pain or tenderness, fever, rash and or eosinophilia (>5%).
- The study will be stopped if one subject meeting Hy's Law is detected (i.e. ALT or AST >3x ULN and total bilirubin >2x ULN and no other reason can be found to explain the combination of increased AT and TBL, such as viral hepatitis A, B, or C; preexisting or acute liver disease; or another drug capable of causing the observed injury).
- Individual reports of exacerbations of Crohn's disease CTCAE Grade 3 or greater, such as:
 - Colonic or ileal hemorrhage
 - Colonic, ileal or small intestine obstruction
 - Colonic, ileal or small intestine perforation
 - Colonic, ileal or small intestine stenosis

will be reviewed by the DMC at the first available date after report to determine if modifying the study or stopping the study is recommended.

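### The infection stopping item in Protocol 8.5.1 and 8.5.2, read literally, covers only tuberculosis; 'i.e.' should be 'e.g.'

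*Protocol*

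**What the plan says.** Protocol 8.5.1 lists events which, at CTCAE Grade 3 or higher, meet the individual-subject stopping criteria. The infection entry is "Opportunistic infections (i.e. tuberculosis", followed by a closing parenthesis. Section 8.5.2 repeats the entry word for word in the study-level list. That list opens "The study will be stopped if two or more subjects develop the same CTCAE Grade 3" and adds a second trigger, one subject with a Grade 4 event.

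The next entry in both lists is "Hypersensitivity reactions (e.g. allergic reactions, anaphylaxis or cytokine release syndrome", where 'e.g.' introduces examples. The Hy's Law entry in both sections explains its term after 'i.e.': "i.e. ALT or AST >3x ULN and total bilirubin >2x ULN and no other reason can be found".

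Section 8.3 (Safety Data Review) lists reactions that deserve special attention. Its infection entry is "Potential for increased infection including opportunistic infections (such as tuberculosis", so there tuberculosis is one example of the class.

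Section 8.8 makes assignment to the second dose cohort conditional on the 8.5.2 criteria not having been met, alongside DMC review and a sponsor decision.

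**The concern.** In a stopping rule, site staff and the sponsor apply the words as printed. Table 1 has staff assess the 8.5.1 criteria from the first dose through Visit 10, and the study may run at up to 20 centers. If one reader takes the item as tuberculosis only and another takes it as the whole class, the same event would be handled differently.

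The item matters in this population. Section 10.2.1 allows prednisone up to 40 mg/day, with azathioprine, 6-MP or methotrexate, alongside the study drug. Doses are 14 days apart and SAP 5.3 gives a half-life of 18.0 to 27.0 days, so a further dose given while a decision is pending cannot be undone quickly. Safety and tolerability are the primary objective.

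Tuberculosis is also the infection that screening already tries to remove. A history of tuberculosis, active disease or a positive screening test excludes a subject (9.2 and 9.4, item 12; 12.3.1.5.3). Read literally, the rule covers mainly what has been screened out and leaves other opportunistic infections with no stopping item.

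**Working it through.** No arithmetic in the plan bears on this: the sample size rests on feasibility and the documents give no infection rate. The check is of wording and coverage.

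**1. Is the literal reading available?** Within 8.5, 'e.g.' introduces examples (hypersensitivity) and 'i.e.' introduces a definition (Hy's Law). Elsewhere the protocol also uses 'i.e.' to define. Section 12.3.1.5.6 explains what undetectable means, 6.3 identifies the first-cohort dose, and 9.6 identifies the end-of-treatment visit. A careful reader could therefore take tuberculosis as the definition of the item.

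**2. Is the class defined anywhere else?** No readable text in the protocol or SAP defines opportunistic infection or says that the stopping item extends beyond tuberculosis. The reaction list in 12.3.1.6.7.1 is redacted, and the Investigator's Brochure and DMC charter are not among the documents.

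**3. Does another stopping item catch infection?**
- The CTCAE items in 8.5.1 are injection site reaction, opportunistic infection, hypersensitivity, malignancy, white cells, neutrophils, platelets, hemorrhage, obstruction, perforation and stenosis. That is 11, of which 1 is infection.
- The study-stop list in 8.5.2 has the first 7 of these, of which 1 is infection.
- The liver and Hy's Law rules do not concern infection. The DMC-review bullet in 8.5.2 concerns disease exacerbation.

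**4. What does each reading do with a non-tuberculous opportunistic infection?**

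| Event | Subject criterion, literal | Subject criterion, class | Study stop, literal | Study stop, class |
|---|---|---|---|---|
| Grade 3, one subject | not met | met | no | no |
| Same Grade 3, two subjects | not met | met | no | yes |
| Grade 4, one subject | not met | met | no | yes |

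The readings differ at subject level in all three rows. At study level they differ only in the last two; a single Grade 3 stops the study under neither.

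**5. What follows for escalation?** Section 8.8 refers to 8.5.2. If either of the last two events occurred in the first cohort before escalation, the literal text would leave the stopping-criteria condition satisfied. The wider gate in 6.3, which requires that no important safety finding has arisen in the first cohort, would still apply, but as a judgement.

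**6. How mandatory is each rule?** Section 8.5.2 says that the study will be stopped. Section 9.6 lists meeting the 8.5.1 criteria among the reasons for which the investigator has the right to withdraw a subject. The loss of a mandated stop is therefore clearest in 8.5.2.

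**The case against.** The strongest reply is that this is a copy-editing slip that nobody would follow. The entry names a plural class; a rule meant for one disease would simply name it. Section 8.3, in the same chapter, treats tuberculosis as an example. Because tuberculosis is screened out and follow-up ends at about Day 84, a tuberculosis-only item would almost never apply. This is persuasive about intent, and it stands: the broad meaning is the likely one. It does not remove the need for a correction, because the narrow reading fits how the section uses 'i.e.' elsewhere.

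The second reply is that other safeguards would catch a serious case. Investigators review safety data weekly (8.3) and may withdraw a subject (9.6). SAEs reach the sponsor and CRO within 24 hours (12.3.1.6.6.1), and a Grade 4 infection would ordinarily be serious. The medical monitor can involve the DMC as needed (8.3), the DMC can adjust its meeting schedule (8.4), and the sponsor can end the study at any time (8.9). This also stands, and it limits the severity. These routes bring a case to attention but leave stopping to judgement, which 8.5.2 was written to avoid.

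The third reply is that 'e.g.' does not make the rule fully automatic. Whether an event is opportunistic remains a clinical call, and the text does not say whether two different opportunistic infections count as the same Grade 3 event. Both points are correct.

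A reader might go further and size the problem by DMC timing. The ad hoc meetings that 8.4 names are "ad hoc meetings to assess individual exacerbations of CD or UC meeting Common Terminology Criteria for Adverse Events" at Grade 3 or greater, and 10.1 puts the second-cohort review "after all subjects have completed the treatment period and its associated assessments". From this one might infer that the 3 mg/kg subjects as a group are left unprotected. The documents do not support that as a measure of this defect. The meeting schedule is the same whichever abbreviation is printed. SAP 13 says the DMC "will review the study data at separate meetings after enrollment in the first and second cohorts, respectively", which could fall earlier, and 8.4 allows the schedule to change.

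**Conclusion.** The point holds as a wording defect in an operative safety rule, of low-to-moderate severity. Taken literally, the item excludes every opportunistic infection except tuberculosis from the subject criteria, from the mandated study stop, and from the stopping-criteria condition in 8.8.

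Three stronger conclusions might be inferred and are not supported:
- **That the sponsor chose a tuberculosis-only rule.** The protocol gives no rationale for one, and 8.3 points the other way.
- **That 8.3 and 8.5 give conflicting instructions.** One governs surveillance and the other stopping; they differ only in how they gloss a shared term.
- **That serious infections would go unnoticed or unmanaged.** The reporting and review routes would bring them to the sponsor; what is lost is the mandate to stop.

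The wording is certain. The practical effect is less so: it needs a qualifying event, a literal reading by whoever applies the rule, and a decision not to stop under the discretionary safeguards. With no event rate in the documents, no expected number of affected subjects can be given. The conclusion also assumes that the redacted list, the Investigator's Brochure and the DMC charter do not define the class for the stopping rule.

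**What to change.** In the infection bullet of both 8.5.1 and 8.5.2, replace 'i.e.' with 'e.g.' or 'including', in line with 8.3. Leave the grade thresholds as they are. Notify the sites and the DMC of the corrected wording without waiting for other changes.

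If a tuberculosis-only rule was in fact intended, the item should say tuberculosis and the protocol should give the reason. The same amendment could usefully state whether two different opportunistic infections count as the same event for the two-subject trigger, since the change of abbreviation does not settle that.

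The cost is one abbreviation in two bullets at the next amendment, plus a notice. The small downside is that the stopping rules may trigger somewhat more often.
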